# 8.2 Stopping rules

*Death and life-threatening adverse events*: Drug dosing in further participants will be held pending IRB review, if any subject develops any grade IV or V (death) adverse events (Common Terminology Criteria for Adverse Events [CTCAE] version 4.0 or equivalent, see http://ctep.cancer.gov/reporting/ctc.html) considered possibly or definitely related to plerixafor within 10 days of administration of the drug.

*Non-pain crisis related events:* The allowance of a 20% rate for grade III AEs (attributable to plerixafor) is reasonable, given that 30-40% of participant's experience headaches or GI symptoms after plerixafor and a minority of these adverse events might lead to a grade III AE. Drug dosing in further participants will be held pending IRB review, if stopping rules are met in Table 2. Both pain crisis and acute chest syndrome are considered in a separate set of stopping rules below.

We examined the performance of the stopping rule against a range of true non-pain grade III (or higher) AE probabilities – between 10% and 50%. This range was chosen to span plausible AE rates based on clinical experience. The probability of concluding whether the regimen is unsafe (or safe) was determined by the percentage of 100,000 simulated trials in which the stopping rule boundary was reached (or not reached) for a given AE probability. Each simulated trial involved generating 15 dichotomous (yes/no) AE outcomes with the given AE probability and it was determined if the cumulative count of AEs reached the stopping boundary. The boundary was chosen after considering a range of different possible combinations of sample sizes and stopping boundaries. This boundary was selected because the performance balances a strong probability of stopping the trial when the true AE rate is too high (30% or more) and allowing the trial to continue when the AE rate is relatively low (less than 20%).

Table 2 – Stopping rule: Stop if 2 non-pain grade 3 or higher AEs observed in first 5 individuals, 4 AEs after evaluating 6-10 individuals, or 5 AEs after evaluating 11-15 individuals

True, Unknown AE probability	Probability Conclude Safe	Probability Conclude Unsafe
0.50	0.04	0.96
0.40	0.14	0.86

0.30	0.37	0.63
0.20	0.67	0.33
0.15	0.81	0.19
0.10	0.91	0.09

*Pain crisis related events*: Pain crisis is excluded from the criteria of grade III, while acute chest syndrome is included as grade III or IV. We anticipate up to a rate of 40% for pain crisis (attributable to plerixafor). This rate reflects that among the patients with SCD that have undergone allogeneic HSCT at our center, approximately 30-35% have chronic pain requiring chronic opioid usage and had frequent hospitalizations for pain at baseline. This prevalence is similar to the sickle cell center in Milwaukee, where 34 of 115 patients had 5-11 hospitalizations per year and 17 patients had  $\geq 12.^{36}$  Additionally, all the patients in our current gene therapy study (14-H-0155) had at least 4-5 days of hospitalization after marrow harvest, indicating that pain induced by the harvest procedure is substantial in all patients. The pain from plerixafor would be expected to be lower. Thus, we define pain crisis for this protocol to be (1) duration of hospitalization for the entire HSC collection (e.g. from plerixafor to discharge) to be more than 4 days due to pain that is considered to be sickle related crisis; or (2) hospitalization for pain crisis after discharge from the initial HSC collection and within 10 days of the final plerixafor dose; or (3) escalation in pain treatment (e.g. from oral to IV narcotics administration or from as needed doses of IV to PCA narcotics)..

Hence drug dosing in further participants will be held pending IRB review, if stopping rules are met in Table 3.

True, Unknown AE	Probability Conclude Safe	Probability Conclude Unsafe
probability		
0.60	0.03	0.97
0.50	0.13	0.87
0.40	0.36	0.64
0.30	0.66	0.34
0.20	0.90	0.10

Table 3 – Stopping rule: Stop if 3 pain AEs (defined above) observed in first 5 individuals, 5 AEs after evaluting 6-10 individuals, or 6 AEs after evaluating 11-15 individuals.

The boundaries for pain AEs were determined in a manner similar to the boundary for grade III AEs. Participants will be dosed sequentially, with no overlap during the 10-day monitoring period, (including hospital admission to clinic visit post-stem cell collection) to allow assessment of adverse events in each participant before proceeding to the next. If stopping rules are met at 240 ug/kg, dose reduction may be proposed at that time.

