# 8.0 Biostatistical Considerations

# 8.1 Sample size

This is a pilot study of safety of plerixafor mobilization in SCD. This study will accrue a maximum of 15 SCD patients at plerixafor 240  $\mu$ g/kg-and safety will be determined by successful accrual without reaching stopping rules.

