#### 9.0 Data Safety and Monitoring Plan

The side effects of plerixafor mobilization and apheresis should be less than that of G-CSF, which are well described and vast experience with the procedure in both normal volunteers and family donors exists in the Clinical Center. In addition, we will evaluate for vaso-occlusive crisis for SCD

patients, for which vast experience also exists in the Clinical Center. Grade 3 and higher AEs and SAEs will be collected from the start of first dose of plerixafor administration to 10 days after the last dose of plerixafor. For subjects enrolled at the NIH, AEs and SAEs outside of this window of time will be tracked on the natural history protocol (04-H-0161), screening protocol (08-H-0156), or transplant protocol (03-H-0170, 14-H-0077, 17-H-0069).

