# 9.6.4 Serious Adverse Events (SAEs) Reporting

All Serious Adverse Events (SAEs) will be tracked for 30 days or until resolution, or until the end of study (10 days after last dose of the study treatment).

SAEs, CTCAE Grade 3 and above, and all subsequent follow-up reports will be reported to the Safety Monitoring Committee (DSMC) using the study specific CRF regardless of the event's relatedness to the investigation. Following review by the DSMC, events meeting the IRB definition of 'Unanticipated Problem' will be reported to the IRB using eProtocol within 10 working days of DSMC review, or within 5 working days for deaths or life-threatening experiences.

SAEs, within 24 hours (US) or one business day (EU) of first knowledge of such serious adverse event, will need to notify Sanofi via fax, attention Sanofi Pharmacovigilance (PV), [contact] (US) or via email at: [contact]. Additionally, the Investigator will transmit to Sanofi PV an information copy of any such report sent to the governing regulatory authority, prior to or at the time of authority filing. The Investigator will make available to Sanofi promptly such records as may be necessary and pertinent to investigate any such expedited adverse event, if specifically requested by Sanofi.

Furthermore, the Investigator will inform Sanofi of the following:

- Any events that result in protocol amendments for safety reasons, as well as any safety related regulatory action such as a clinical hold of the Research;
- Any pregnancies occurring in patients who are exposed to the Product in connection with the Research.
- In addition, the Investigator will notify Sanofi within 24 hours (US) or one business day (EU) of first knowledge of any Product complaints (communication of dissatisfaction that alleges deficiencies related to the identity, quality, durability, effectiveness, safety, labeling, purity, stability, and appearance) by fax to [contact] (US) or Sanofi Customer Services Europe, [name].
- The Investigator will also inform Sanofi within 1 business day of becoming aware of any actions from any authority that may affect the performance of the Research

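### Section 8.2 gives conflicting instructions on whether plerixafor-related grade III acute chest syndrome counts toward the Table 2 stopping boundary

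*Combined protocol and SAP*

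**What the plan says.** Section 8.1 makes the stopping rules the safety criterion: "safety will be determined by successful accrual without reaching stopping rules". Section 8.2 then sets three rules, each leading to a hold on further dosing pending IRB review.

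- **Single-event rule.** Any grade IV or V event possibly or definitely related to plerixafor within 10 days of dosing.
- **Table 2, non-pain events.** "Stop if 2 non-pain grade 3 or higher AEs observed in first 5 individuals", with 4 events in participants 6-10 and 5 in participants 11-15. The text allows a 20% rate of attributable grade III events.
- **Table 3, pain events.** "Stop if 3 pain AEs (defined above) observed in first 5 individuals", with 5 in participants 6-10 and 6 in participants 11-15. The text anticipates a rate of up to 40%.

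Two sentences place acute chest syndrome (ACS). The Table 2 paragraph says "Both pain crisis and acute chest syndrome are considered in a separate set of stopping rules below". The Table 3 paragraph opens with "Pain crisis is excluded from the criteria of grade III, while acute chest syndrome is included as grade III or IV". It then defines a pain crisis in three ways: a collection stay of more than 4 days because of sickle pain, readmission for pain crisis within 10 days of the final dose, or escalation of pain treatment. None of the three mentions ACS.

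**The concern.** One sentence takes ACS out of the Table 2 count and the other keeps it in. Someone who follows the first goes to Table 3 and finds a count of pain events whose definition ACS does not by itself meet. A related, exactly grade III ACS with no qualifying pain event (called residual ACS below) would then count in neither table.

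This matters because reaching or not reaching a boundary is the study's stated safety result, and the early boundary is tight. Two related grade III ACS events among the first five participants would hold dosing if ACS counts in Table 2. Under the literal reading of the first sentence they would trigger nothing unless a pain criterion was also met.

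**Working it through.** **Step 1: reproduce the printed tables.** Let S2(p) be the probability that the cumulative count over 15 sequential participants reaches 2 (participants 1-5), 4 (6-10) or 5 (11-15), and S3(p) the same for 3/5/6. Exact binomial recursion gives:

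| Rule | True rate | Printed | Exact |
|---|---|---|---|
| Table 2 | 0.50 / 0.40 / 0.30 | 0.96 / 0.86 / 0.63 | 0.963 / 0.857 / 0.632 |
| Table 2 | 0.20 / 0.15 / 0.10 | 0.33 / 0.19 / 0.09 | 0.331 / 0.193 / 0.088 |
| Table 3 | 0.60 / 0.50 / 0.40 | 0.97 / 0.87 / 0.64 | 0.972 / 0.872 / 0.647 |
| Table 3 | 0.30 / 0.20 | 0.34 / 0.10 | 0.342 / 0.103 |

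All agree within 0.01. The boundaries and their operating characteristics are sound. Only the definition of what is counted is at fault.

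**Step 2: Table 2 result under the two readings.** Reading A counts residual ACS in Table 2 and reading B does not. Inputs are other grade III events at o = 0.20 (the allowance in 8.2) and residual ACS at rate a, independent of the other events. The value of a is an assumption. The per-participant rate under A is 1 − (1 − o)(1 − a), and under B it is o. A's count is never below B's, so every trial held under B is also held under A. The share of trials that differ is therefore

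D = S2(1 − (1 − o)(1 − a)) − S2(o).

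For a = 0.01, the rate under A is 1 − 0.80 × 0.99 = 0.208, and D = 0.3544 − 0.3305 = 0.0239.

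**Step 3: whether dosing is ever held under either table.** A difference on Table 2 matters for the hold only if Table 3 has not been reached. With independent pain events at 40% the factor is 1 − S3(0.40) = 1 − 0.6468 = 0.3532. At 30% it is 0.658, and at 20% it is 0.8975.

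| Residual ACS (assumed) | Rate under A | Table 2 differs (D) | Ever held differs, pain 40% | pain 30% | pain 20% |
|---|---|---|---|---|---|
| 1% | 0.208 | 2.39% | 0.85% | 1.57% | 2.15% |
| 2% | 0.216 | 4.82% | 1.70% | 3.17% | 4.32% |
| 5% | 0.240 | 12.20% | 4.31% | 8.03% | 10.95% |
| 10% | 0.280 | 24.38% | 8.61% | 16.04% | 21.88% |

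Values are computed before rounding. Residual ACS by definition excludes qualifying pain in the same participant. Imposing that while keeping the overall pain rate at 40% moves the ever-held figures to 1.05 / 2.12 / 5.36 / 10.56%.

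**Step 4: no ACS rate assumed.** Take exactly one residual ACS, in a participant with no other counted event. If it falls among the first five, then by participant 5 reading A holds with probability 1 − 0.8⁴ = 0.5904. Reading B holds with probability 1 − 0.8⁴ − 4 × 0.2 × 0.8³ = 0.1808. The gap at that point is 0.4096. Over all 15 participants:

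| Position of the event | Table 2 differs, other 20% | Ever held differs (pain 40%) | Table 2 differs, other 10% | Ever held differs (pain 40%) |
|---|---|---|---|---|
| 1-5 | 39.5% | 14.0% | 29.7% | 10.5% |
| 6-10 | 11.4% | 4.0% | 2.9% | 1.0% |
| 11-15 | 8.4% | 3.0% | 1.7% | 0.6% |

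The single-event grade IV/V rule is not modelled, and a difference in the timing of a hold is not counted.

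**The case against.** The strongest reply is that the gap opens only on a partial reading. The first sentence points below, and the first line of the paragraph below places ACS at grade III or IV. Table 2's non-pain caption agrees. That stands as evidence of intent, but it also confirms the fault: under that reading ACS has no separate rule, and the sentence saying it does is wrong.

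A second reply is that ACS may have been meant for Table 3, so that the omission lies in the pain definition. The choice would matter. For ACS alone at 10% or 20%, the Table 2 boundary is reached with probability 0.09 or 0.33 and the Table 3 boundary with 0.01 or 0.10. This reading is weaker, because the later sentence contrasts ACS with the pain crisis that it excludes from grade III, and Table 3 counts only pain as defined.

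Third, the rates have no anchor in the documents. Residual ACS is a narrow event in patients transfused or exchanged toward HbS below 30%, so the 5% and 10% rows deserve little weight. At 1% or 2%, 0.99¹⁵ = 86% or 0.98¹⁵ = 74% of 15-participant trials would have no such event. The 20% is an allowance, not a forecast. With other events at 10%, the ever-held difference at 40% pain is 0.6% or 1.2%. All of this stands.

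Fourth, little depends on it now. Section 10.3 records that accrual is closed and only data analysis continues. A boundary meant a hold for IRB review, not termination. ACS also remains visible: "Grade 3 and higher AEs and SAEs will be collected from the start of first dose of plerixafor administration" (section 9.0), the DSMB reviews safety data (9.1), and SAEs are reported regardless of relatedness (9.6.4). This too stands, and it is why the point is minor.

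**Conclusion.** The conflict is real, and the sentence in the Table 2 paragraph is wrong as written. Its reach is limited to related, exactly grade III ACS without qualifying pain. Related grade IV or V ACS triggers the single-event hold under either reading, and ACS with qualifying pain still counts in Table 3.

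At assumed residual rates of 1-2%, the stated Table 2 result changes in about 2-5% of trials and the fact of a hold in about 1-2%. These figures rest on independence and on the protocol's 20% and 40% rates. One such event among the first five participants would matter much more (39.5% for Table 2, 14.0% for ever being held). The difference is zero if no residual ACS occurred, or if it occurred only in participants already counted in Table 2. No dosing decision can change now. What remains is that the Table 2 result be reported under one stated rule. Severity: minor.

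**What to change.** In the non-pain paragraph of section 8.2, remove the reference to acute chest syndrome so that only pain crisis is sent to the separate rules. Related grade III ACS then counts in Table 2, as the pain paragraph already implies, and grade IV or V ACS stays under the single-event rule. Neither boundary nor either printed table changes.

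Because accrual is closed, also report the cumulative Table 2 count in dosing order with related grade III ACS included, and list any ACS by grade and relatedness, or state that none occurred.

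The cost is one phrase in the protocol and one line in the safety report, with no new data and no further participants.

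### The Table 2 count boundary skips a step after participant 5, so it holds dosing at 2 of 5 but not at 3 of 7, which is stronger evidence of harm (minor)

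*Combined protocol and SAP*

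**What the plan says.** Section 8.1 plans at most 15 participants and states that "safety will be determined by successful accrual without reaching stopping rules". Section 8.2 then gives the count rule for non-pain grade III or higher events in the caption of Table 2: "Stop if 2 non-pain grade 3 or higher AEs observed in first 5 individuals, 4 AEs after evaluating 6-10 individuals". For the last five participants the threshold rises to 5. Reaching it holds further dosing pending IRB review.

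The benchmark is stated in the same section: "The allowance of a 20% rate for grade III AEs (attributable to plerixafor) is reasonable". The boundary is said to have been selected, after other combinations were considered, for balancing a high chance of stopping at true rates of 30% or more against continuing below 20%. Its performance was simulated as 15 yes/no outcomes with a cumulative count. Participants are dosed one at a time, without overlap of the 10-day monitoring periods.

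Table 3 has a parallel rule for pain crises: "Stop if 3 pain AEs (defined above) observed in first 5 individuals, 5 AEs after evaluting 6-10 individuals". Its threshold for the last five participants is 6. A separate rule in 8.2 holds dosing after any single grade IV or V event judged possibly or definitely related to plerixafor.

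**The concern.** A count boundary should not stop on one result and continue on a worse one. Table 2 moves from 2 events to 4 with no step at 3. A trial that has just passed participant 5 could see events in both participants 6 and 7, stand at 3 of 7, and meet no count threshold, although 2 of 5 would have held it. The plan's one-at-a-time dosing exists so that each participant's events are assessed before the next is dosed, so a gap straight after the first step matters. Section 8.1 also ties the safety conclusion to whether a boundary is reached, so the shape of the boundary is part of the main analysis.

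**Working it through.** **Inputs** (all from 8.1 and 8.2): n = 15; Table 2 thresholds 2, 4, 5 for participants 1-5, 6-10, 11-15; benchmarks 20% (allowed) and 30% (too high); Table 3 thresholds 3, 5, 6, with an anticipated pain-crisis rate of up to 40%.

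**1. Reproduce the printed figures.** Let S_n(k) be the probability of k events after n participants with no hold so far. Then S_n(k) = (1-p)·S_{n-1}(k) + p·S_{n-1}(k-1), and any mass at or above the threshold for participant n is moved to the held total. The held total after participant 15 is:

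- Table 2, true rates 0.50/0.40/0.30/0.20/0.15/0.10: 0.963/0.857/0.632/0.331/0.193/0.088. Printed: 0.96/0.86/0.63/0.33/0.19/0.09.
- Table 3, true rates 0.60/0.50/0.40/0.30/0.20: 0.972/0.872/0.647/0.342/0.103. Printed: 0.97/0.87/0.64/0.34/0.10.

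Both tables are right for their captions, within simulation error.

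**2. Where the count rule can act.** A trial that passes participant 5 has at most 1 event. Reaching 4 needs three more, so participant 8 is the earliest. At a 30% rate the cumulative hold probability is 0.472 after participant 5 and unchanged after 6 and 7. A trial that passes participant 10 has at most 3 events and needs two more to reach 5, so participant 11 is also silent (0.536 after both 10 and 11). One silent participant follows any one-event step up. The two-event jump is what makes two in a row, at 6 and 7.

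**3. Strength of evidence.** Tail = P(X ≥ k) for X binomial(n, p0). Posterior = P(rate > p0) under Beta(1+k, 1+n-k), that is, a uniform prior.

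| State | Table 2 action | Observed rate | Tail, 20% | Posterior >20% | Tail, 30% | Posterior >30% |
|---|---|---|---|---|---|---|
| 2/5 | hold | 40% | 0.263 | 0.901 | 0.472 | 0.744 |
| 3/7 | none | 43% | 0.148 | 0.944 | 0.353 | 0.806 |
| 3/8 | none | 37.5% | 0.203 | 0.914 | 0.448 | 0.730 |
| 4/11 | none | 36% | 0.161 | 0.927 | 0.430 | 0.724 |

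3/7 exceeds 2/5 on every measure. 3/8 and 4/11 are clearly stronger only against 20%. Against 30% their posteriors fall slightly below that of 2/5, their tails lean slightly the other way, and their observed rates are lower.

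**4. How often.** An unheld 3/7 needs exactly 1 event in the first 5, then events in both 6 and 7: 5p(1-p)^4·p². At p = 0.30 this is 0.360 × 0.09 = 0.032; at 0.40 it is 0.259 × 0.16 = 0.041. Including 3/8, the figures are 4.5%, 8.2% and 9.6% of trials at true rates of 20%, 30% and 40%. At 30%, 23% of those trials still finish without a hold (0.082 × 0.23 ≈ 0.019). At 40%, 10% do (0.096 × 0.10 ≈ 0.010).

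**5. Adding the missing step.** Keep 2 in 1-5, then 3 in 6-8, 4 in 9-11, 5 in 12-15. The same recursion gives P(conclude unsafe):

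| True rate | 0.50 | 0.40 | 0.30 | 0.20 | 0.15 | 0.10 |
|---|---|---|---|---|---|---|
| Plan | 0.963 | 0.857 | 0.632 | 0.331 | 0.193 | 0.088 |
| With step | 0.967 | 0.871 | 0.658 | 0.356 | 0.212 | 0.097 |

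Expected number dosed is the sum over participants of the probability of not yet being held. At 30% it falls from 9.16 to 8.77. The increase at 20% is 0.3564 - 0.3305 = 0.026; at 10% it is 0.009.

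On the posterior scale, once at least two events have occurred, every state this rule holds then ranks above every state it passes, against both 20% and 30%. The margin against 20% is thin: 4/12, passed, falls just below 2/5, and both round to 0.901. On the binomial tail at 20%, 4/12 (0.205), 4/13 (0.253) and marginally 3/9 (0.262) still sit below 2/5 (0.263), so the ordering is not repaired on every scale.

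**6. Table 3.** Posterior P(rate >40%): 3/5 (hold) 0.821, 4/7 (none) 0.826, 5/11 (none) 0.665, 6/15 (hold) 0.527. The early inversion is 0.005.

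**The case against.** The strongest defence is that 8.2 never claimed step-to-step consistency. The boundary was chosen on overall stopping probabilities, alternatives were considered, and those probabilities are disclosed correctly. A strict first step is reasonable when section 3.0 says the risks of plerixafor in sickle cell disease are not known. Most of the stopping power sits there by design (0.472 of 0.632 at a 30% rate). Filling the gap exchanges more false holds for more detection, which is a trade-off rather than the repair of an error. The effect is small, and section 10.3 says accrual closed in February 2019.

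Most of that stands, and it is why the point is minor. What it does not explain is 3/7: a strict first step gives no reason to continue on a worse result two participants later, and the stated balance does not require the gap.

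The rule's silence at participants 6 and 7 should not be read as no protection there. The grade IV/V hold still operates, the DSMB may recommend termination (9.1), and an unexpected frequency or severity of events must be reported (9.5). Reaching Table 2 is itself a hold pending review, not termination.

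**Conclusion.** The Table 2 interim hold is inconsistent: it acts at 2/5 and not at the reachable, stronger 3/7. An unheld 3/7 arises in about 3% of trials at a true 30% rate and 4% at 40%. Severity is minor.

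A reader might infer that the final safety verdict passes stronger evidence of harm than it stops on. The documents do not support that. The verdict in 8.1 is given on completed accrual, and the worst completed count that passes is 4/15 (tail at 20% 0.352, posterior >20% 0.798), which is weaker evidence than 2/5 (0.263 and 0.901). A reader might also extend the point to Table 3. There the difference between 3/5 and 4/7 is trivial. A one-step alternative (3 in 1-4, 4 in 5-7, 5 in 8-11, 6 in 12-15) would leave 3/5 (0.821) unheld while still holding 6/15 (0.527). No change to Table 3 is supported.

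The result assumes independent participants with a common event probability, one yes/no outcome each, the count checked after every participant, and dosing ended at the first hold. The posterior figures also assume a uniform prior.

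**What to change.** Reconcile the Table 2 steps. One way is to keep the 2-of-5 hold, insert the missing step (for example 3 in 6-8, 4 in 9-11, 5 in 12-15), and reprint Table 2 with the values above. Otherwise, state in 8.2 why a count of 3 is passed over. The cost is one caption, one re-run table, no extra participants, and 0.9 to 2.6 percentage points more holds pending IRB review at true rates of 20% or less.

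A boundary of 2 in 1-4, 3 in 5-8, 4 in 9-11 and 5 in 12-15 matches the plan's printed probabilities closely but is not recommended. It removes the 2-of-5 hold, so holds by participant 5 at a 30% rate fall from 0.472 to 0.348, and it doses more participants on average at every printed rate.

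With accrual closed, no boundary should be applied retrospectively. The report should give the sequence of events by participant alongside the verdict, say whether 3/7 was passed through, and correct the steps if the rule is reused.
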